6.1. Primary Objective

This study is divided into 3 parts:

Part A: to investigate safety and tolerability of pembrolizumab 200 mg Q3W when combined with necitumumab administered at the doses of 600 mg and 800 mg on Days 1 and 8 of 21-day cycles in patients with Stage IV NSCLC (all histologies) as measured by number of patients with a DLT during Cycle 1

Part B: to evaluate the efficacy of necitumumab in combination with pembrolizumab in terms of ORR by RECIST 1.1 in patients with Stage IV NSCLC of squamous and nonsquamous histology

Part C: to investigate safety and tolerability of pembrolizumab 200 mg Q3W when combined with necitumumab administered at the recommended dose from Part A in Japanese patients with Stage IV NSCLC of squamous and nonsquamous histology as measured by number of patients with a DLT during Cycle 1

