A treatment cycle will be defined as 21 days. Study therapy, consisting of necitumumab plus pembrolizumab, will continue until there is a radiographic documentation of PD, toxicity requiring cessation, protocol noncompliance, or withdrawal of consent. Discontinuation of treatment may be considered for patients who have attained a confirmed CR that have been treated for at least 24 weeks from Cycle 1 Day 1 with pembrolizumab and necitumumab or pembrolizumab alone and had at least 2 treatments with pembrolizumab with or without necitumumab beyond the date when the initial CR was declared.

Part C:

Part C will only enroll patients from Japan. It is a single-arm study to evaluate safety and tolerability of necitumumab at the recommended dose identified from Part A of the study on Days 1 and Day 8 Q3W in combination with pembrolizumab 200 mg on Day 1 Q3W in Japanese patients with stage IV NSCLC (Figure JFCQ.8.1).

Part C will first enroll 6 patients. If 2 out of 6 patients experience DLTs, the sponsor will examine the safety data and consult with an external committee as needed. The sponsor will decide if the dose is intolerable, or if additional patients will be enrolled to the same dose level (or lower dose level) for further investigation. If additional patients are needed, 6 additional Japanese patients will be enrolled (to maximum of 12 Japanese patients in Part C).

Terms used to describe the periods during the trial are defined below:

- **Baseline:** begins when the ICF is signed and ends at the first study treatment (or at discontinuation, if no treatment is given).
- **Study Period:** begins at the first study treatment and ends at study completion. The study period does not include the continued access period.
 - **Study Treatment Period:** begins at the first study treatment and ends when the patient and the investigator agree that the patient will no longer continue study treatment. The date of this agreement is to be reported on the case report form (CRF) as the Date of Discontinuation from study treatment.
- **Postdiscontinuation Follow-Up:** begins the day after the patient and the investigator agree that the patient will no longer continue study treatment.

Short-term follow-up begins the day after the patient and the investigator agree that the patient will no longer continue study treatment and lasts approximately 30 days.

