9.4.1. Special Treatment Considerations

9.4.1.1. Dose-Limiting Toxicity (Parts A and C)

A DLT is defined as one of the following AEs, occurring in Cycle 1 if considered to be definitely, probably, or possibly related to necitumumab and pembrolizumab. The following list will define DLT:

- Grade 3 or 4 nonhematologic toxicity according to the NCI-CTCAE Version 4.0, except for skin toxicity, nausea, vomiting, diarrhea, or electrolyte disturbance (see below). For patients with \leq Grade 2 hepatic transaminase levels at baseline as a result of liver metastases, a transaminase level ≥ 10 x ULN lasting for >7 days will be considered a DLT.
- Grade 4 nausea, vomiting, or diarrhea that persists more than 3 days despite maximal supportive intervention
- Grade 3 thrombocytopenia with bleeding requiring transfusion
- Grade 4 thrombocytopenia with or without bleeding
- Grade 4 neutropenia that persists more than 5 days
- Grade 3 or 4 neutropenia with fever, defined as single temperature of $>38.3^{\circ}\text{C}$ (101°F) or a sustained temperature of $\geq 38^{\circ}\text{C}$ (100.4°F) for more than one hour
- Grade ≥ 3 skin toxicity despite best supportive care, with exception of Grade 3 rash that resolves to Grade ≤ 2 within 14 days with appropriate supportive therapy
- If a total at least 75% of the planned dose for both agents cannot be administered in the first cycle due to toxicity
- Prolonged delay (>2 weeks) in initiating cycle 2 due to treatment-related toxicity
- Grade 5 toxicity

DLT is defined by sponsor and principal investigator.

The following toxicities will not be considered DLTs if they are transient (<7 days):

- Hypersensitivity and injection site reactions (If a Grade 3 or 4 hypersensitivity/IRR to necitumumab or pembrolizumab occurs, this event will not be considered a DLT; the patient will not receive any further study therapy and will be replaced in the study by a new patient.)
- Grade ≥ 3 myalgia, fatigue, or constipation, with full supportive therapy
- Grade ≥ 3 increase or decrease of electrolytes
- Grade 3 nausea, vomiting, or diarrhea that resolves to Grade ≤ 1 within 7 days of appropriate supportive therapy
- Grade ≥ 3 elevation of serum creatine kinase level that is asymptomatic that returns to Grade ≤ 2 within 21 days of necitumumab treatment interruption

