Laboratory/ Diagnostic Tests	Att. 2	Hematology	X	X		Investigator-designated (local) laboratory can be used to perform additional tests for on-study dosing decisions. If so, the test must also still be performed by the central laboratory. Pretreatment laboratory data may not be older than 72 hours (Day 1 of each cycle) or 24 hours (Day 8). Hepatic monitoring tests (see Site Guidance Document for DILI) to be done in the event of a treatment-emergent hepatic abnormality. In case of neutropenia, thrombocytopenia Grade 4 during Cycle 1 (dose finding part only), repeat every 2 days until recovery.
	Att. 2	Chemistry	X	X		Investigator-designated (local) laboratory can be used to perform additional tests for on-study dosing decisions. If so, the test must also still be performed by the central laboratory. Pretreatment laboratory data may not be older than 72 hours (Day 1 of each cycle) or 24 hours (Day 8). Hepatic monitoring tests (see Site Guidance Document for DILI) to be done in the event of a treatment-emergent hepatic abnormality. Grade 3 elevation of transaminases, bilirubin, change of electrolytes (see DLT criteria), repeat every 2 days until recovery.
	Att. 2	Coagulation (central)	X*			* To be performed every second cycle starting from Cycle 2
	Att. 2	T3, free T4, TSH (central)	X*			* To be performed every second cycle starting from Cycle 2
	Att. 2	Urinalysis (local)	X*			* To be performed every second cycle starting from Cycle 2
	Att. 2	Pregnancy test (local)	X*			Local urine test can be performed. If the urine test is positive or cannot be confirmed as negative, a serum pregnancy test will be required. * To be performed every cycle in women of childbearing potential
	10.3.4	PK sampling (central)	Refer to Attachment 6.			
	10.3.3	Immunogenicity: Anti-necitumumab antibodies	Note: If a patient experiences an IRR to necitumumab at any time during the study, blood samples for both immunogenicity and PK analysis should be drawn, with no more than 15 minutes' time difference. Samples will be taken at the following time points: (1) as soon as possible after the onset of the IRR, (2) at the resolution of the IRR, and (3) 30 days after the IRR.			
	10.3.2	Plasma and Whole blood samples for Biomarker Analysis	Refer to Attachment 6.			
	10.3.2.1	Whole blood for genetic evaluation	Refer to Attachment 6.			
10.2.2.1	ECG (local)	X*			* To be performed every second cycle starting from Cycle 2	

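### Part C uses the same DLT definition as Part A, but the repeat counts that would show how long a Grade 4 neutropenia lasts are required only in an undefined dose finding part

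*Protocol*

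**What the plan says.** Protocol Section 6.1 sets the primary objective of Part C as safety and tolerability "in Japanese patients with Stage IV NSCLC of squamous and nonsquamous histology as measured by number of patients with a DLT during Cycle 1". Section 8.1 starts Part C with 6 patients and attaches a formal step to the count: "If 2 out of 6 patients experience DLTs, the sponsor will examine the safety data".

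Section 9.4.1.1 is headed as applying to Parts A and C and gives a single DLT list for both. One item is "Grade 4 neutropenia that persists more than 5 days". The platelet item has no duration: "Grade 4 thrombocytopenia with or without bleeding".

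The Treatment Period Schedule in Attachment 1 marks hematology on Days 1 and 8 of each cycle. Its comment adds: "In case of neutropenia, thrombocytopenia Grade 4 during Cycle 1 (dose finding part only), repeat every 2 days until recovery". The chemistry comment in the next row has the same 2-day repeat, refers to the DLT criteria, and carries no restriction to a part.

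The term *dose finding part* is defined nowhere and appears only in that comment. Section 8.1 calls Part A the dose-escalation part and describes Part C as DLT confirmation at the dose taken from Part A.

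SAP Section 5.6.3 says that DLTs will be listed for Part A only, although SAP Section 4.1 gives Part C the same DLT-based primary objective.

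**The concern.** A criterion defined by duration cannot be decided from one blood count. Part A has a rule that produces the further counts. On the natural reading of the comment, Part C does not, although it uses the same definition for its primary measure.

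At stake is the classification of a Part C patient in whom Grade 4 neutropenia is found. Without required repeats, a neutropenia lasting more than 5 days may go uncounted, or a short one may be called a DLT because nobody can show that it was short. With 6 patients and a trigger at 2, each classification carries weight.

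**Working it through.** The documents state no error rate or operating characteristic for Part C, so there is no figure to reproduce. The check sets the schedule against the criterion.

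**1. Which criteria need serial counts.** In Section 9.4.1.1, Grade 4 thrombocytopenia is a DLT on one count, and febrile neutropenia needs a count and a temperature. Of the blood-count items, only Grade 4 neutropenia beyond 5 days needs a measured duration.

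**2. Required counts in Part C, Cycle 1.** These are Day 1 (pre-dose), Day 8 (pre-dose) and Cycle 2 Day 1 (nominal Day 22). The gap after Day 8 is 22 − 8 = 14 days, and 14 / 5 = 2.8 times the threshold. If the Day 8 visit runs 3 days late, the gap is 22 − 11 = 11 days. The window on the Cycle 2 visit and the 72-hour laboratory allowance can shorten it further.

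**3. What those counts can show.** Assume onset is uniform over the 21 days from Day 1 to Day 22 (my assumption; the documents give no onset data). An episode of L days, with L no more than 14, is seen on Day 8 with probability min(L, 7)/21 and on Day 22 with probability L/21.

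| Episode length | Seen once | Seen at neither | Seen twice |
|---|---|---|---|
| 6 days | (6 + 6)/21 = 57% | 43% | 0% |
| 7 days | (7 + 7)/21 = 67% | 33% | 0% |
| 10 days | (7 + 10)/21 = 81% | 19% | 0% |

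Seeing an episode at both nominal counts requires it to last more than 14 days. A 15-day episode is seen twice with probability 1/21 = 5%.

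The *seen at neither* column is the same in Part A, because the 2-day repeats begin only once a Grade 4 count has been found. The parts differ in the *seen once* column. Part A then requires counts that bracket recovery to within 2 days, measured from detection and not from onset. Part C requires none.

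**4. Grade 4 found on Day 8.** Sections 9.4.1.2.2 and 9.4.1.2.2.1 hold necitumumab until related hematologic toxicity is Grade 2 or lower, or back to baseline. Section 9.4 lets the Day 8 dose slip by at most 5 days, to Day 8 + 5 = Day 13, after which it is omitted. One of two necitumumab doses is 50%, below the 75% in the dose-delivery DLT item. Read per agent, a related Grade 4 neutropenia lasting more than 5 days from Day 8 therefore becomes a DLT by that route. If the item needs both agents to fall short, it does not, because pembrolizumab was given in full on Day 1.

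**5. Grade 4 found after the Day 8 dose.** The 5-day delay limit no longer applies. Recovery is still required before the next necitumumab dose, but the delay criterion in Section 9.4.1.1 concerns Cycle 2 starting more than 2 weeks late, which is far longer than 5 days.

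**6. Effect on the 2-of-6 trigger.** P(at least 2 of 6) = 1 − (1 − p)^6 − 6p(1 − p)^5. The rates below are assumptions, since the documents give none. They compare a DLT rate without this criterion to one with 1 or 5 percentage points added by it.

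| Rate without | Without | +1 point | +5 points |
|---|---|---|---|
| 10% | 0.114 | 0.134 | 0.224 |
| 20% | 0.345 | 0.369 | 0.466 |
| 30% | 0.580 | 0.601 | 0.681 |

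These differences overstate the loss, because they treat every such DLT as missed and ignore step 4.

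**The case against.** The strongest reply is that the protocol as a whole does not leave a Part C patient with Grade 4 neutropenia unobserved.

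- Re-dosing requires recovery, and recovery cannot be shown without a new count.
- Section 10.2 has related events followed until resolved or explained.
- Sites may add local counts.
- For a Grade 4 count on Day 8, the 5-day delay limit matches the 5-day threshold, so the 75%-of-dose item picks up much the same patients.

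It can also be said that *dose finding part* might be meant to separate the DLT-assessed parts from Part B, since Part C keeps a possible move to a lower dose level.

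Much of this stands. A reader might infer that Part C cannot measure the criterion at all, or that patients go 14 days unmonitored. Neither follows: 14 days is the gap between required counts under the schedule alone.

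The reply does not remove the conflict. Local counts are optional and are offered for dosing decisions. Section 10.2 leaves follow-up frequency to the investigator. The dose-delivery item measures doses given, not how long neutropenia lasted, and it depends on a per-agent reading and on attribution to necitumumab. None of these provisions sets a 5-day limit for a count found after the Day 8 dose. If Part C was meant to be included, the comment still needs to say so.

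**Conclusion.** The point holds in limited form. One DLT definition serves Parts A and C, but the counts that would establish one of its criteria are required only in an undefined part that naturally means Part A. In Part C the duration of a detected Grade 4 neutropenia is therefore not directly ascertained for the primary DLT count.

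The practical size is small and cannot be fixed from the documents. Only the neutropenia duration criterion is affected. No neutropenia rate is given for the combination. The event is probably uncommon: in the Japanese single-agent study described in Section 5.2 (15 patients), no DLT occurred in the first cycle, and the only related events above Grade 2 were dry skin and rash in one patient.

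Three further inferences go too far:

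- **That one misclassified patient decides whether safety is reviewed.** It could move the count from 1 to 2 of 6 and so affect the formal step, but Section 10.2.3 has the sponsor's physician monitoring safety throughout.
- **That Part A detects such episodes and Part C does not.** Episodes wholly between scheduled counts are missed in both.
- **That the comment was simply not updated when Part C was added.** The SAP revision history ties Part C to amendment (a), but the prior protocol text is not available to show this.

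The conclusion rests on reading *dose finding part* as Part A and on the nominal visit days.

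**What to change.** Reconcile Section 9.4.1.1 with the hematology comment in Attachment 1, so that the repeat-count comment covers every part in which the 9.4.1.1 DLT definition is used. Naming Parts A and C in place of the dose finding part would do this. Align SAP Section 5.6.3 so that the DLT listing covers Part C as well as Part A.

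If Part C Cycle 1 data have already been collected, the report should state how neutropenia duration was established for any patient with a Grade 4 count.

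The cost is a few words in each document, plus a few extra blood counts in any Part C patient who develops the event in Cycle 1. The change will not find episodes that fall wholly between scheduled counts, and it does not date onset.

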Attachment 2. Protocol JFCQ Clinical Laboratory Tests

Clinical Laboratory Tests

Hematology^a:

Hemoglobin
 Hematocrit
 Erythrocyte count (RBC)
 Mean cell volume (MCV)
 Mean cell hemoglobin concentration (MCHC)
 Leukocytes (WBC)
 Neutrophils, segmented and bands
 Lymphocytes
 Monocytes
 Eosinophils
 Basophils
 Platelets

Thyroid Function Test^e:

Thyroid-stimulating hormone (TSH)
 Total triiodothyronine (T3)
 Free thyroxine (T4)

Urinalysis^c:

Color
 Specific gravity
 pH
 Protein
 Glucose
 Ketones
 Blood
 Urine leukocyte esterase

Clinical Chemistry^a:

Serum concentrations of:

Sodium
 Magnesium
 Potassium
 Phosphate
 Total bilirubin
 Direct bilirubin
 Alkaline phosphatase
 Alanine aminotransferase (ALT)
 Aspartate aminotransferase (AST)
 Blood urea nitrogen (BUN)
 Creatinine^b
 Uric acid
 Calcium
 Glucose, nonfasting
 Albumin
 Cholesterol
 Creatine kinase (CK)

Pregnancy Test (females of childbearing potential only)^d

Coagulation Tests^e:

INR and PT
 PTT
 Fibrin D dimer
 Protein C activity (baseline only)
 Protein S activity (baseline only)

Abbreviations: IDMS = isotope dilution mass spectrometry; INR = International Normalized Ratio;

PT = prothrombin time; PTT = partial thromboplastin time; RBC = red blood cells; WBC = white blood cells.

- ^a Assayed by Lilly-designated (central) laboratory. Investigator-designated (local) laboratory can be used to perform additional tests for on-study dosing decisions. If so, the test must also still be performed by the central laboratory.
- ^b IDMS for United States sites.
- ^c Assayed by investigator-designated (local) laboratory.
- ^d For fulfilling Inclusion Criterion 12, a central serum pregnancy test is mandatory. During treatment and postdiscontinuation periods, a local urine test can be performed. If the local urine test is positive or cannot be confirmed as negative, a serum pregnancy test will be required.
- ^e Assayed by Lilly-designated (central) laboratory.

Attachment 3. Protocol JFCQ ECOG Performance Status Performance Status

ECOG Performance Status

Activity Status	Description
0	Fully active, able to carry on all pre-disease performance without restriction
1	Restricted in physically strenuous activity but ambulatory and able to carry out work of a light or sedentary nature, e.g., light house work, office work
2	Ambulatory and capable of all selfcare but unable to carry out any work activities. Up and about more than 50% of waking hours
3	Capable of only limited selfcare, confined to bed or chair more than 50% of waking hours
4	Completely disabled. Cannot carry on any selfcare. Totally confined to bed or chair
5	Dead.

Source: Oken et al. 1982.

Attachment 4. Protocol JFCQ Creatinine Clearance Formula

Note: This formula is to be used for calculating creatinine clearance (CrCl) from **local laboratory results only.**

*For serum creatinine
concentration in mg/dL:*

$$\text{CrCl} = \frac{(140 - \text{age}^a) \times (\text{wt}) \times 0.85 \text{ (if female), or } \times 1.0 \text{ (if male)}}{72 \times \text{serum creatinine (mg/dL)}} \\ \text{(mL/min)}$$

For serum creatinine concentration in $\mu\text{mol/L}$:

$$\text{CrCl} = \frac{(140 - \text{age}^a) \times (\text{wt}) \times 0.85 \text{ (if female), or } \times 1.0 \text{ (if male)}}{0.81 \times \text{serum creatinine } (\mu\text{mol/L})} \\ \text{(mL/min)}$$

^a age in years, weight (wt) in kilograms.
Reference: Cockcroft and Gault 1976.

CCI

CCI [REDACTED]

[REDACTED]

[REDACTED]

[REDACTED]

[REDACTED]

[REDACTED]

[REDACTED]

[REDACTED]

[REDACTED]

[REDACTED]

[REDACTED]

[REDACTED]

CCI [Redacted]

[Redacted]

[Redacted]

[Redacted]

[Redacted]

[Redacted]

CCI [Redacted]

[Redacted]

CCI

CCI [Redacted]

[Redacted]

[Redacted]

[Redacted]

[Redacted]

[Redacted]

CCI [Redacted]

[Redacted]

[Redacted]

[Redacted]

[Redacted]

CCI [Redacted]

[Redacted]

[Redacted]

[Redacted]

[Redacted]

[Redacted]

[Redacted]

CCI [Redacted]

[Redacted]	[Redacted]	[Redacted]	[Redacted]
[Redacted]	[Redacted]	[Redacted]	[Redacted]
[Redacted]	[Redacted]	[Redacted]	[Redacted]
[Redacted]	[Redacted]	[Redacted]	[Redacted]

CCI [Redacted]

CCI [REDACTED]

[REDACTED]

CCI [REDACTED]

[REDACTED]

[REDACTED]

[REDACTED]

CCI

CCI [REDACTED]

[REDACTED]

Attachment 6. Protocol JFCQ Pharmacokinetic, Immunogenicity, and Blood-Based Markers Sampling Schedule

PK and Immunogenicity samples will be collected for necitumumab only. It is essential that the exact infusion start and stop times (actual clock readings) are recorded. The exact time of collection of each venous blood sample will be based on the clock used to record infusion times. It is essential that the pharmacokinetic blood samples not be withdrawn from the same I.V. site as the drug infusion.

Predose samples should be taken as close as possible to the start of first infusion, but can be drawn up to 1 hour (60 minutes) prior first infusion, and exact clock reading should be recorded. Post-dose (post-end of infusion) samples for PK for necitumumab should be drawn immediately after end of necitumumab infusion (range = after end of infusion +10 minutes) and exact clock reading should be recorded.

In addition, if a patient experiences an IRR, blood samples for both immunogenicity (anti-necitumumab antibody,) and PK (necitumumab concentration) should be drawn, with no more than 15 minutes' time difference between PK and immunogenicity samples. Samples will be taken at the following time points: (1) as soon as possible after the onset of the IRR, (2) at the resolution of the IRR, and (3) 30 days after the IRR.

Pharmacokinetic, Immunogenicity, Biomarker, and Pharmacogenetic Sample Collection for Part A, Part B, and Part C

Visit/Cycle Day	Study Day	Sample Time (relative to start of pembrolizumab infusion) (HR:MIN) ^a	Necitumumab PK ^c (Serum)	Necitumumab Immunogenicity ^c (Serum)	Biomarker and Pharmacogenetic	
					Plasma and Whole Blood for Biomarker	Whole Blood for Genetics
Cycle 1 Day 1 (Pembrolizumab and Necitumumab infusion)	1	0:00 hr Predose sample ^{b,e}	X (collect prior to start of first infusion)	X	X	X
		1:30 hr Postdose sample ^{d,e}	X (collect immediately after Necitumumab infusion ends)			
Cycle 1 Day 8 (Necitumumab infusion only)	8	0:00 hr Predose sample			X	
Cycle 2 Day 1 (Pembrolizumab and Necitumumab infusion)	22	0:00 hr Predose sample ^{b,e}	X (collect prior to start of first infusion)	X	X	
		1:30 hr Postdose sample ^{d,e}	X (collect immediately after Necitumumab infusion ends)			
Cycle 4 Day 1 (Pembrolizumab and Necitumumab infusion)	64	0:00 hr Predose sample ^{b,e}	X (collect prior to start of first infusion)	X	X	
		1:30 hr Postdose sample ^{d,e}	X (collect immediately after Necitumumab infusion ends)			

Visit/Cycle Day	Study Day	Sample Time (relative to start of pembrolizumab infusion) (HR:MIN) ^a	Necitumumab PK ^c (Serum)	Necitumumab Immunogenicity ^c (Serum)	Biomarker and Pharmacogenetic	
					Plasma and Whole Blood for Biomarker	Whole Blood for Genetics
Cycle 6 Day 1 (Pembrolizumab and Necitumumab infusion)	106	0:00 hr Predose sample ^{b,e}	X (collect prior to start of first infusion)	X	X	
		1:30 hr Postdose sample ^{d,e}	X (collect immediately after Necitumumab infusion ends)			
Cycle 8 Day 1 (Pembrolizumab and Necitumumab infusion)	148	0:00 hr Predose sample ^{b,e}	X (collect prior to start of first infusion)	X	X	
		1:30 hr Postdose sample ^{d,e}	X (collect immediately after Necitumumab infusion ends)			
30 days Post treatment DC		Anytime ^f	X	X	X	

Abbreviations: DC = Discontinuation; eCRF = electronic case report form; PK = pharmacodynamics; IK = immunokinetics/immunogenicity; IRR = infusion-related reaction.

Note: 30-minute pembrolizumab infusion is given first followed by 60-minute necitumumab infusion.

^a All sample times are relative to start of first infusion.

^b Pre-dose sample for necitumumab PK, and/or IK should be preferably collected within 1 hour prior to start of first infusion.

^c In the event of an IRR, blood samples will be collected for necitumumab PK and IK analysis at the following time points within 15 minutes of one another: (i) as close as possible to the onset of the IRR, (ii) at the resolution of the IRR, and (iii) 30 days following the IRR.

^d Postdose samples should be collected after the end of necitumumab infusion, preferably within a 10 minute time window.

^e While best effort should be done to draw the blood sample for PK/IK within the time windows provided above, it is more important to ensure predose sample is actually collected before the start of first infusion and postdose infusion samples are collected after infusion has actually completed. It is also equally important to record ACTUAL date and time of blood collection for PK/IK sample on the Requisition Form AFTER drawing the sample and to accurately record the ACTUAL infusions start and end dates and times on the eCRF to be able to use the data for analyses. Sample collection for PK/IK must be from the opposite arm to that used for study drug infusion. If drug was administered via a central venous catheter, the sample collection should be from a different site.

^f Record ACTUAL date and time of blood collection for PK/IK sample on the Requisition Form AFTER drawing the sample. PK/IK sample should be taken within 15 minutes of one another.

**Attachment 7. Protocol Amendment I4X-MC-JFCQ(d)
Summary An Open-Label, Multicenter, Phase 1b Study with
an Expansion Cohort to Evaluate Safety and Efficacy of the
Combination of Necitumumab with Pembrolizumab in
Patients with Stage IV Non-Small Cell Lung Cancer**

Overview

Protocol I4X-MC-JFCQ, An Open-Label, Multicenter, Phase 1b Study with Expansion Cohorts to Evaluate Safety and Efficacy of the Combination of Necitumumab with Pembrolizumab in Patients with Stage IV Non-Small Cell Lung Cancer, has been amended. The new protocol is indicated by amendment (d) and will be used to conduct the study in place of any preceding version of the protocol.

The overall change and rationale for the change made to this protocol are as follows:

- A second dosage form is available for pembrolizumab. Details of the pembrolizumab solution for infusion (100 mg/vial) have been added to Section 2 (Synopsis) and Section 9.2 (Materials and Supplies).

Revised Protocol Sections

Note: Deletions have been identified by ~~strikethroughs~~.
Additions have been identified by the use of underscores.

2. Synopsis

Test Product, Dosage, and Mode of Administration:

- Necitumumab is a sterile, preservative-free, intravenous infusion supplied in 50-mL vials containing 16 mg/mL (800 mg/50 mL) of product, and administered over 60 minutes at a dose of 600 mg or 800 mg on Days 1 and 8 of each 21-day cycle.
- Pembrolizumab drug product is available in 2 dosage forms intended for intravenous administration: dosage form ~~is~~ a lyophilized powder, 50 mg/vial, ready to be reconstituted with sterile water for injection prior to use, and a liquid, 100 mg/vial, both in Type I glass vials intended for single use only. Pembrolizumab is ~~and~~ administered over 30 minutes (-5 min/+ 10 min) at a dose of 200 mg on Day 1 of each 21-day cycle.

